7.2.4.3 Serum Pharmacodynamic Assay Methodology

Serum sample analysis will be performed according to relevant Standard Operating Procedures at the contract bioanalytical lab (inVentiv Health).

Serum PD concentrations will be measured using the most current validated bioanalytical methods. In addition, selected serum samples may be used to investigate incurred sample reproducibility (full details will be described in the bioanalytical study plan). The presence of other metabolites or artifacts may be monitored or quantified as appropriate.

7.2.5 Immunogenicity Testing for Anti-Parathyroid Hormone Antibodies

The name and address of the bioanalytical laboratory (Covance) conducting anti-PTH immunogenicity testing for this study will be maintained in the investigator's files at the each site and in the Trial Master File at the sponsor.

Actual anti-PTH blood sample collection times versus time of dosing will be monitored. The sponsor's expectation is that the investigator will ensure that every effort is made to collect all anti-PTH blood samples at the precise protocol scheduled time. Anti-PTH blood collection will be collected on Day 1 prior to dose (within 30 minutes of dose) and at the follow-up visit.

In the event anti-PTH antibodies are detected following analysis for a subject, the investigator will be notified by the sponsor. It will be the investigator's responsibility to notify the subject.

7.2.5.1 Sample Collection and Handling Procedures for Immunogenicity Testing for Anti-Parathyroid Hormone Antibodies

Blood samples will be collected at the time specified in [Table 1](#), to detect anti-PTH antibodies in serum. A full description of the anti-PTH blood collection, handling, storage and shipping can be found in the provided laboratory manual. Serum sample tubes for bioanalysis must be freezer-safe and identified with freezer-safe labels provided by the CRC. The labels will contain the following information:

- Study number: SHP634-102
- Subject identifier
- Nominal day
- Nominal time
- Matrix identifier (serum)
- Split (primary or back-up)

7.2.5.2 Anti-Parathyroid Hormone Antibody Assay Methodology

Serum sample analysis will be performed according to relevant Standard Operating Procedures at the contract bioanalytical lab (Covance).

Detection of anti-PTH antibodies from serum blood samples will use the most currently validated bioanalytical method.

7.2.6 Volume of Blood to Be Drawn from Each Subject

Table 4 Volume of Blood to Be Drawn from Each Subject

| | | Caucasian | | Japanese | |
|--|--|--------------------|-------------------|-------------------|-------------------|
| Assessment | | Sample Volume (mL) | Number of Samples | Total Volume (mL) | Number of Samples |
| Pharmacokinetic samples ^a | | 4 | 18 | 72 | 54 |
| Serum PTH sample ^a | | 2 | 2 | 4 | 2 |
| Pharmacodynamic samples ^a | | 6 | 5 | 30 | 15 |
| HBsAg, HIV, HCV ^a | | 8.5 | 1 | 8.5 | 1 |
| Safety | Biochemistry, FSH and β -hCG ^{a, b} | 8.5 | 5 | 42.5 | 9 |
| | Hematology ^a | 4 | 5 | 20 | 9 |
| Anti-PTH Antibody Samples ^a | | 3 | 2 | 6 | 2 |
| Total mL | | | | 183 | 437 |

β -hCG=beta-human chorionic gonadotropin; FSH=follicle stimulating hormone, HBsAg=hepatitis B surface antigen; HCV=hepatitis C virus; HIV=human immunodeficiency virus

^a If a catheter is in use for any blood draw or series of blood draws then the first 1mL is to be discarded. The 1mL discard has been taken into account in the table above and the total blood volume required for study.

^b β -hCG and FSH testing for females only.

During this study, it is expected that approximately 437mL of blood will be drawn from all subjects of Japanese descent, regardless of sex. For the non-Hispanic, Caucasian volunteers it is expected that 183mL of blood will be drawn, regardless of sex.

Note: The amount of blood to be drawn for each assessment is an estimate. The amount of blood to be drawn may vary according to the instructions provided by the manufacturer or laboratory for an individual assessment; however, the total volume drawn over the course of the study

should be approximately 183mL (non-Hispanic, Caucasian subjects) or 437mL (subjects of Japanese descent). When more than 1 blood assessment is to be done at the time point/period, if they require the same type of tube, the assessments may be combined.

8. ADVERSE AND SERIOUS ADVERSE EVENTS ASSESSMENT

8.1 Definition of Adverse Events, Period of Observation, Recording of Adverse Events

An **AE** is any untoward medical occurrence in a clinical investigation subject administered a pharmaceutical product and that does not necessarily have a causal relationship with this treatment. An **AE** can therefore be any unfavorable and unintended sign (including an abnormal laboratory finding), symptom, or disease temporally associated with the use of a medicinal (investigational) product, whether or not related to the medicinal (investigational) product (International Conference on Harmonisation [ICH] Guidance E2A 1995).

All AEs are collected from the time the informed consent is signed until the defined follow-up period stated in Section 7.1.3. This includes events occurring during the screening phase of the study, regardless of whether or not investigational product is administered. Where possible, a diagnosis rather than a list of symptoms should be recorded. If a diagnosis has not been made, then each symptom should be listed individually. All AEs should be captured on the appropriate source documents. In addition to untoward AEs, unexpected benefits outside the investigational product indication should also be captured on the AE source documentation.

All AEs must be followed to closure (the subject's health has returned to his/her baseline status or all variables have returned to normal), regardless of whether the subject is still participating in the study. Closure indicates that an outcome is reached, stabilization achieved (the investigator does not expect any further improvement or worsening of the event), or the event is otherwise explained. When appropriate, medical tests and examinations are performed so that resolution of event(s) can be documented.

8.1.1 Severity Categorization

The severity of AEs must be recorded during the course of the event including the start and stop dates for each change in severity. An event that changes in severity should be captured as a new event. Worsening of pretreatment events, after initiation of investigational product, must be recorded as new AEs (for example, if a subject experiences mild intermittent dyspepsia prior to dosing of investigational product, but the dyspepsia becomes severe and more frequent after first dose of investigational product has been administered, a new AE of severe dyspepsia [with the appropriate date of onset] is recorded in the source documentation).

The medical assessment of severity is determined by using the following definitions:

Mild: A type of AE that is usually transient and may require only minimal treatment or therapeutic intervention. The event does not generally interfere with usual activities of daily living.

Moderate: A type of AE that is usually alleviated with specific therapeutic intervention. The event interferes with usual activities of daily living, causing discomfort but poses no significant or permanent risk of harm to the research subject.

Severe: A type of AE that interrupts usual activities of daily living, or significantly affects clinical status, or may require intensive therapeutic intervention.

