9.9.2 Statistical Methodology for Safety Endpoint(s)

Safety data, including TEAEs, laboratory tests, anti-PTH antibodies, and vital signs, will be summarized. Descriptive statistics will be calculated for quantitative safety data as well as for the difference from baseline, if applicable. Frequency counts will be compiled for classification of

qualitative safety data. Direct safety comparisons between the two ethnic groups will be presented from the rhPTH(1-84) 100µg dosing data. All other safety data from the 25µg and 50µg in the subjects of Japanese descent will be summarized and listed. Treatment-emergent AEs (TEAEs) are defined as AEs whose onset occurs, severity worsens, or intensity increases after receiving the study medication of this study to the follow-up visit.

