11.1 Adverse Events

Adverse events will be coded using Version 20.0 or newer of MedDRA.

An AE (classified by preferred term) that occurs during the study will be considered a TEAE if it has a start date/time on or after the first dose of investigational product or if it has a start date before the date of the first dose of investigational product, but increases in severity or intensity on or after the date/time of the first dose of investigational product. If more than 1 AE with the same preferred term is reported before the date of the first dose of investigational product, then the AE with the greatest severity will be used as the benchmark for comparison to the AEs occurring during the study under the preferred term. An AE that occurs after follow-up visit will not be counted as a TEAE. However, any SAE that occurs after the follow-up visit and is considered related should be counted as a TEAE.

Adverse events will be allocated to a dose by assigning them to the last dose taken at the time of the onset of the AE.

An overall summary of the number of subjects with TEAEs will be presented by ethnic group and dose at onset, including the number and percentage of subjects with any TEAEs, serious TEAEs, TEAEs related to investigational product, TEAEs leading to discontinuation of investigational product, severe TEAEs, and deaths.

The number and percentage of subjects reporting TEAEs for each ethnic group and dose at onset will be tabulated by system organ class (SOC) and preferred term; and by SOC, preferred term, and maximum severity. TEAEs considered related to investigational product will also be summarized by SOC and preferred term. If more than 1 AE occurs with the same preferred term for the same subject, then the subject will be counted only once for that preferred term using the most severe occurrence for the summarization by severity. Serious TEAEs and TEAEs leading to discontinuation of investigational product will be summarized by SOC, preferred term, ethnic group and dose at onset.

Listings will be produced for all AEs (including pre-treatment AEs), SAEs, AEs considered related to investigational product, AEs leading to discontinuation of investigational product, and deaths.

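### An adverse event that is still present at the next dose and then eases to a lower grade is counted again under that later dose in Japanese subjects

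*Protocol*

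**What the plan says.** Protocol 8.1.1 (Severity Categorization) asks for severity to be recorded through the course of an event, "including the start and stop dates for each change in severity", and then states: "An event that changes in severity should be captured as a new event". No direction is given. The sentence that follows does name a direction, "Worsening of pretreatment events, after initiation of investigational product, must be recorded as new AEs", but it concerns only events present before treatment and does not narrow the general rule.

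SAP 11.1 (Adverse Events) contains two further rules. An adverse event "will be considered a TEAE if it has a start date/time on or after the first dose of investigational product"; an event that began earlier qualifies if it later worsens. Events are allocated to a dose "by assigning them to the last dose taken at the time of the onset of the AE". The TEAE tables are laid out by ethnic group and dose at onset. Where a subject has several events with one preferred term, SAP 11.1 counts the subject once for that term, but does not say whether this works within a dose column or across columns.

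Under SAP 2.1, all Japanese subjects receive 100 µg on Day 1 and then 25 and 50 µg in randomized order on Days 4 and 7, with 72 to 73 hours between doses. Caucasian subjects receive one 100 µg dose.

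**The concern.** The recording rule gives an improving event a fresh start date, and the allocation rule uses that date to choose the dose. Nothing in SAP 11.1, or in the adverse event conventions of SAP 18.6 to 18.8, ties the lower-grade record back to the event it came from.

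Safety and tolerability at 25, 50 and 100 µg in Japanese subjects is a secondary objective, and the protocol synopsis says the results will guide dose selection for a Phase 3 study in Japanese patients. Because 100 µg always comes first, any carry-over out of that dose runs from the highest dose into the two lower-dose columns, which would tend to flatten a dose trend. A Day 4 event can pass into the Day 7 dose in the same way. Only the Japanese group changes dose, so these cross-dose repeats can arise only there. Each new record also needs its own causality assessment (Protocol 8.1.2), so the table of related events is exposed too.

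**Working it through.** The plan states no figure to reproduce. The check applies the written rules to example event courses.

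**Inputs from the documents.** Doses are taken at 0, 72 and 144 hours (72-hour minimum interval, SAP 2.1). There are 12 Japanese subjects (SAP 2.5). A new record starts at each severity change (Protocol 8.1.1). A record is a TEAE if it starts on or after first dose, and it belongs to the most recent dose at its start (SAP 11.1).

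**Assumptions.** The event courses and their times are illustrative; the documents give none.

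| Course after the Day 1 dose | Rules as written | Improving records keep original onset and dose |
|---|---|---|
| Moderate at 2 h, mild at 80 h | 2 events: 100 µg and Day 4 dose | 1 event: 100 µg |
| Severe at 2 h, moderate at 80 h, mild at 150 h | 3 events: 100 µg, Day 4 dose and Day 7 dose | 1 event: 100 µg |
| Moderate at 2 h, mild at 60 h | 2 events, both 100 µg; subject counted once | 1 event: 100 µg |
| Mild at 2 h, resolves at 80 h | 1 event: 100 µg | 1 event: 100 µg |

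The first two courses place the subject in a later dose column. The last two do not: a step-down at 60 h comes before the Day 4 injection, and resolution creates no new grade. Three conditions are therefore needed together: the event is still present at the next injection, it steps down after that injection, and the lower grade is not zero.

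**Size per subject.** In a column of 12, one carried-over subject adds 1/12 = 8.3 percentage points to a preferred-term incidence, and two add 2/12 = 16.7.

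**Does once-per-term counting remove the repeat?** Only if it works across doses. The tables are by dose at onset, so the natural reading is within a column. SAP 9 points the same way for medications: it counts multiple use in a category once, yet lets a medication belong to more than one dose. Counting subjects once would in any case leave the number of events, which Protocol 9.9 also asks for, unchanged.

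**The case against.** The strongest reply is that the situation should be rare and the consequence small. These are healthy volunteers given single doses. Protocol 3.2 gives a terminal half-life of about 1 to 2 hours and a return to baseline PTH at about 12 hours, so few events should last 72 hours and then ease by a grade. The direct ethnic safety comparison uses the 100 µg data only; the 25 and 50 µg data are descriptive, and SAP 2.6 calls the statistical analyses exploratory. The error over-counts events and hides none. All events are listed, so a reader could spot contiguous same-term records among 12 subjects. Allocation to the most recent dose is also a simple, prespecified rule.

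The points on rarity and impact stand, and they limit the weight of this comment. They do not correct the tables: a listing lets a reader find the error but leaves the tabulated incidence wrong.

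Three stronger readings are tempting and are not supported.

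- A reader might infer that the SAP contradicts Protocol 9.9.2, which covers events "whose onset occurs, severity worsens, or intensity increases after receiving the study medication". Onset after dosing is sufficient there too, just as the start date is in the SAP. The two definitions diverge only if onset means record onset in one document and onset of the underlying event in the other, which neither says.
- A reader might infer that pre-dose events that ease after the Day 1 injection inflate the 100 µg ethnic comparison. The start-date criterion alone would admit such a record. But SAP 11.1 also uses the greatest pre-dose severity as a benchmark for later events under the same term, at least where more than one such event was reported before dosing. How the two rules interact is ambiguous. A caffeine-withdrawal headache is a poor example, because exclusion criterion 14 removes subjects who experience them. Inflation at 100 µg is possible but not shown.
- A reader might infer that any resolving 100 µg event is counted twice. The worked courses show otherwise.

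**Conclusion.** The point holds in limited form. Followed exactly, Protocol 8.1.1 and SAP 11.1 together place an improving event under a dose at which it did not begin. This is a stated rule giving a wrong allocation, not a missing detail. It affects the Japanese 25 and 50 µg columns, including a Day 4 event passing into the Day 7 dose.

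The 8.3 points is one subject's share of a 12-subject column. It is not an estimate of bias, because the frequency is unknown and probably low. The conclusion rests on two readings: that a severity change in either direction makes a new record, as the text says without qualification, and that once-per-term counting operates within a dose column. If that counting were meant across columns, the repeat would drop out of subject counts but remain in event counts. The change is worth making because it is cheap and these columns serve a stated objective.

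**What to change.** Add three short statements to SAP 11.1:

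1. Contiguous records of the same event that differ only by an unchanged or lower severity keep the original onset and the original dose at onset. A record is newly attributed to a later dose only if severity or intensity rises above its level before that dose.
2. Once-per-preferred-term counting applies within each dose column.
3. The same rule applies at first dose, so a pre-dose event that is improving is not a TEAE. This settles the ambiguity between the start-date criterion and the pre-dose severity benchmark.

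The cost is SAP wording and a step in the adverse event programming that links adjoining stop and start records of one term within a subject. A few records will need manual confirmation that they are one event. Because the study is open-label, the criteria for that confirmation should be written down before the tables are run. Data collection and study conduct do not change.

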8.1.2 Relationship Categorization

A physician/investigator must make the assessment of relationship to investigational product for each AE. The investigator should decide whether, in his or her medical judgment, there is a reasonable possibility that the event may have been caused by the investigational product. If there is no valid reason for suggesting a relationship, then the AE should be classified as “not related”. Otherwise, if there is any valid reason, even if undetermined or untested, for suspecting a possible cause-and-effect relationship between the investigational product and the occurrence of the AE, then the AE should be considered “related”. The causality assessment must be documented in the source document.

The following additional guidance may be helpful:

| Term | Relationship Definition |
|-------------|---|
| Related | The temporal relationship between the event and the administration of the investigational product is compelling and/or follows a known or suspected response pattern to that product, and the event cannot be explained by the subject's medical condition, other therapies, or accident. |
| | |
| Not Related | The event can be readily explained by other factors such as the subject's underlying medical condition, concomitant therapy, or accident and no plausible temporal or biologic relationship exists between the investigational product and the event. |

8.1.3 Outcome Categorization

The outcome of AEs must be recorded during the course of the study on the source documentation. Outcomes are as follows:

- Fatal
- Not Recovered/Not Resolved
- Recovered/Resolved
- Recovered/Resolved With Sequelae
- Recovering/Resolving

- Unknown

8.1.4 Clinical Laboratory and Other Safety Evaluations

A change in the value of a clinical laboratory, vital sign, or ECG assessment can represent an AE if the change is clinically relevant or if, during treatment with the investigational product, a shift of a parameter is observed from a normal value to an abnormal value, or a further worsening of an already abnormal value. When evaluating such changes, the extent of deviation from the reference range, the duration until return to the reference range, either while continuing treatment or after the end of treatment with the investigational product, and the range of variation of the respective parameter within its reference range, must be taken into consideration.

If, at the end of the treatment phase, there are abnormal clinical laboratory, vital sign, or ECG values which were not present at the pretreatment value observed closest to the start of study treatment, further investigations should be performed until the values return to within the reference range or until a plausible explanation (eg, concomitant disease) is found for the abnormal values.

The investigator should decide, based on the above criteria and the clinical condition of a subject, whether a change in a clinical laboratory, vital sign, or ECG parameter is clinically significant and therefore represents an AE.

8.1.5 Pregnancy

All pregnancies are to be reported from the time informed consent is signed until the defined follow-up period stated in Section [7.1.3](#).

Any report of pregnancy for any female study participant or the partner of a male study participant must be reported within 24 hours to the Shire Global Pharmacovigilance and Risk Management Department using the Shire Investigational and Marketed Products Pregnancy Report Form. A copy of the Shire Investigational and Marketed Products Pregnancy Report Form (and any applicable follow-up reports) must also be sent to the contract research organization (CRO)/Shire medical monitor using the details specified in the [emergency contact information](#) section of the protocol. The pregnant female study participant must be withdrawn from the study.

Every effort should be made to gather information regarding the pregnancy outcome and condition of the infant. It is the responsibility of the investigator to obtain this information within 30 calendar days after the initial notification and approximately 30 calendar days post partum.

Pregnancy complications such as spontaneous abortion/miscarriage or congenital abnormality are considered SAEs and must be reported using the Shire Clinical Study Serious Adverse Event and Non-serious AEs Required by the Protocol Form. Note: An elective abortion is not considered an SAE.

In addition to the above, if the investigator determines that the pregnancy meets serious criteria, it must be reported as an SAE using the Shire Clinical Study Serious Adverse Event and Non-serious AEs Required by the Protocol Form as well as the Shire Investigational and

Marketed Products Pregnancy Report Form. The test date of the first positive serum/urine β -hCG test or ultrasound result will determine the pregnancy onset date.

8.1.6 Abuse, Misuse, Overdose, and Medication Error

Abuse, misuse, overdose, or medication error (as defined below) must be reported to the sponsor according to the SAE reporting procedure whether or not they result in an AE/SAE as described in Section 8.2. Note: The 24-hour reporting requirement for SAEs does not apply to reports of abuse, misuse, overdose, or medication errors unless these result in an SAE.

The categories below are not mutually exclusive; the event can meet more than 1 category.

- **Abuse** – Persistent or sporadic intentional intake of investigational product when used for a nonmedical purpose (eg, to alter one's state of consciousness or get high) in a manner that may be detrimental to the individual and/or society
- **Misuse** – Intentional use of investigational product other than as directed or indicated at any dose (Note: this includes a situation where the investigational product is not used as directed at the dose prescribed by the protocol)
- **Overdose** – Intentional or unintentional intake of a dose of investigational product higher than the protocol-prescribed dose
- **Medication Error** – An error made in prescribing, dispensing, administration, and/or use of an investigational product. For studies, medication errors are reportable to the sponsor only as defined below.

Medication errors should be collected/reported for all products under investigation.

The administration and/or use of an expired investigational product should be considered as a reportable medication error.

The administration of rhPTH(1-84) to an eligible volunteer following an excursion in temperature requirements (outlined in the pharmacy manual), without assessment of the excursion and permission of the sponsor to proceed, is deemed a medication error.

It is not expected that overdose would occur in this protocol. The investigative product used in this study is supplied in 1 strength only, and is administered once only per volunteer, by a trained and responsible staff member at the study site with sponsor oversight.

